**Sample size calculation**

8302 nulliparous women are planned to be include demonstrating a 50% reduction of development of PE (from 1.5%). Assuming a 10% loss, the investigators estimated a sample size of 9132 women.

*R Syntax:*

```
library(SampleSize4ClinicalTrials)

ssc_propcomp (1L,ratio=1,alpha=0.05,power=0.9,p1=0.0075, p2=0.015)
```

Under a non-inferiority hypothesis testing design, assuming a composite adverse neonatal outcome incidence of 1% in the revealed group, 0.5% in the concealed risk and a prespecified non-inferiority margin of 0.25%; this sample size (4151 per arm) would result in a power of 99% to reject the null hypothesis that the reveal strategy increases the neonatal complications.

*R Syntax:*

```
library(SampleSize4ClinicalTrials)

ssc_propcomp (3L,ratio=1,alpha=0.05,power=0.99,p1=0.005, p2=0.01, delta=0.0025)
```

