
Estimated Sample Size
 
8302 nulliparous women are needed to demonstrate a 50% reduction of development of PE (from 1.5%) with a 90% power and a 5% alpha-risk. Assuming a 10% loss, we estimated a sample size of 9132 women.

Study Aims
 
To evaluate the impact of a policy of induction of labour from 37 weeks of gestation in nulliparous women at risk for preeclampsia as defined by a sFlt1/PlGF ratio >90th centile at 35-36 weeks of gestation on the prevalence of term PE.
 
As secondary objectives, the study will evaluate the impact of the sFlt1/PlGF screening on:
 
 
Cesarean section rates
 
Perinatal morbidity
 
Maternal pregnancy-related morbidity.
 
Maternal post-pregnancy endothelial function.
 
Cost-efficiency analysis (hospital maternal and neonatal stay and incurred costs).
 
Maternal experience.
 

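### The 10% loss allowance was applied as 8302 × 1.1, not 8302 / 0.9, so 9132 recruits do not leave the 8302 women required

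*Protocol*

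**What the plan says.** The sample size appears twice in the protocol.

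- **Synopsis, Estimated Sample Size.** It presents 8302 nulliparous women as the number needed to show a halving of preeclampsia from 1.5%, "with a 90% power and a 5% alpha-risk". It then adds: "Assuming a 10% loss, we estimated a sample size of 9132 women".
- **Methodology, Sample size calculation.** It repeats 8302 as the planned number and continues: "Assuming a 10% loss, the investigators estimated a sample size of 9132 women". The R call beneath it begins "ssc_propcomp (1L,ratio=1,alpha=0.05,power=0.9,p1=0.0075, p2=0.015". The non-inferiority paragraph that follows gives the per-arm figure as 4151.

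Neither place shows how 8302 became 9132, or says of what total the 10% is a share.

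**The concern.** A loss allowance exists so that the required number of women is still available after losses. Only women who have been recruited can be lost, so a 10% loss ordinarily means 10% of recruits, and the required number is divided by 0.9. Multiplying it by 1.1 gives too few. The figure 9132 looks like the result of that multiplication.

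If so, four figures stated together do not fit: 8302 evaluable women, 10% loss, 9132 recruits and 90% power. These are the trial's headline numbers, they will be carried into reports, and a reader can check them in one line.

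**Working it through.** **Inputs, all from the protocol.** Event rates 0.75% and 1.5%, 1:1 allocation, alpha 0.05 and power 0.90 (R call in Sample size calculation); 8302 in total, 10% loss and 9132 recruits (synopsis and Sample size calculation); 4151 per arm (Sample size calculation). The protocol does not say whether alpha is one- or two-sided.

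**Step 1: reproduce the base number.** Two-sided comparison of two proportions with unpooled variance:

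n per arm = (z₀.₉₇₅ + z₀.₉₀)² × [p₁(1 − p₁) + p₂(1 − p₂)] / (p₁ − p₂)²

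= (1.960 + 1.2816)² × (0.0075 × 0.9925 + 0.015 × 0.985) / 0.0075² = 4150.4, rounded up to 4151.

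Twice 4151 is 8302, an exact match. The pooled-variance version gives 4154 per arm. A one-sided test gives 3383 (unpooled) or 3386 (pooled), and a two-sided continuity correction gives 4417. The protocol's figure is therefore the two-sided, unpooled, uncorrected one, and 8302 is the number that must remain to give 90% power.

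**Step 2: reproduce 9132.** 8302 × 1.1 = 9132.2, which is the stated figure.

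**Step 3: apply the stated loss.** 9132 × 0.9 = 8218.8, about 8219 women. The shortfall is 8302 − 8218.8 = 83.2, and 83.2 / 8302 = 1.0%.

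**Step 4: loss that 9132 can absorb.** 9132 − 8302 = 830 women, and 830 / 9132 = 9.09%.

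**Step 5: recruits needed for a 10% loss.** 8302 / 0.9 = 9224.4, rounded up to 9225, or 9226 for two equal arms. That is 93 or 94 more than 9132, about 1.0%.

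**Step 6: power at the stated loss.** With 8218.8 / 2 = 4109.4 per arm, power = Φ(|p₁ − p₂| / SE − 1.960), where SE = √{[p₁(1 − p₁) + p₂(1 − p₂)] / n}.

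| Evaluable per arm | Power, unpooled | Power, pooled |
|---|---|---|
| 4151 (as planned) | 90.0% | 90.0% |
| 4109.4 (9132 less 10%) | 89.7% | 89.7% |

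**The case against.** The strongest reply is that the gap is immaterial. It costs 0.3 points of power, less than other choices in the same calculation. Moving from the unpooled formula to a continuity-corrected one changes the size by about 6% (4417 against 4151 per arm). If the control rate were 1.4% instead of 1.5%, with the same halving, the Step 1 formula would ask for about 4450 per arm, and power at 4151 would be about 87.9%. That argument stands, and it is why this is only a minor correction. It does not make the stated figures agree.

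A second reply is that the text never says 10% of what. If the 10% is a share of the required 8302, a margin of 830 women, then 9132 is right. That reading is possible but is not the ordinary meaning of loss. If it is the one intended, the text should say so, because the tolerated loss among recruits is then 9.1%.

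A third reply is that 10% is a round planning assumption and real loss of the primary outcome may be lower. Analysis is by intention to treat, outcomes are abstracted from medical records, and data collected before withdrawal are kept. This is fair: any loss up to 9.09% leaves 8302. It bears on how likely a shortfall is, not on whether 9132 meets the allowance the protocol states.

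**Conclusion.** The concern holds. Taking loss as a share of women recruited, 9132 is too small for the stated 10% by 93 recruits, which leaves 83 evaluable women (1.0%) too few and gives 89.7% power instead of 90.0%. The base of 8302 is sound if the test is two-sided, which the protocol does not state but which its own figure implies. The effect on the trial is very small and the primary analysis is not at risk. This is a correction to stated figures, not a finding that the trial is underpowered.

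**What to change.** Keep 9132 and change the sentence about loss in both the synopsis and the Sample size calculation section. Either of these would be accurate:

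- *Recruiting 9132 women allows for the loss of 830 of them (about 9.1%) while retaining the required 8302.*
- *Recruiting 9132 women gives 89.7% power if 10% are lost (about 4109 evaluable per arm).*

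It would help to add that alpha is two-sided. The cost is wording only, with no change to recruitment, design or analysis.

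The alternative is to keep the 10% and the 90% and raise the target to 9225, or 9226 for equal arms. That means enrolling 93 or 94 more women for 0.3 points of power, and it is not necessary. Whichever is chosen, the two sections must be changed together so that they stay consistent.

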### **IOL at 37 weeks as an intervention in women at high-risk for PE.**

Previous trials based on statins have failed to show a reduction of PE in high-risk women. IOL at 37 weeks is an alternative to avoid PE in those high-risk women. IOL has consistently been demonstrated to be safe (13) and does not affect long-term maternal quality of life (14). Both the HYPITAT and the DIGITAT randomized trials showed that IOL did not increase

caesarean rates or adverse neonatal outcomes (15). A recent large randomized trial in the US has shown that even in low-risk women, universal IOL decreased cesarean section rates and was well accepted (16). While in low-risk pregnancies labour induction has been found to be beneficial from 39 weeks (ARRIVE study), in women with placental-related conditions such as hypertension (HYPITAT) or small-for-gestational age (DIGITAT) it is 37+ weeks when the trade-off between neonatal and maternal benefits makes induction recommendable.

Therefore, the investigators hypothesize that a single-step universal screening for term PE based on sFlt1/PIGF ratio at 35-36.6 w followed by IOL at 37w in those women found to be at high risk might represent a feasible and reproducible strategy, applicable worldwide, to reduce the prevalence of term PE without increasing cesarean section rates or adverse neonatal outcomes.

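### The 99% power for neonatal non-inferiority does not follow from the rates stated: 1% (revealed) against 0.5% (concealed) with a 0.25-point margin gives about 0.15%, and 99% appears only with the rates reversed.

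*Protocol*

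**What the plan says.** The Protocol's section Sample size calculation has two parts. The first sizes the trial on preeclampsia, falling from 1.5% to 0.75%, and gives 8302 women (4151 per arm) before losses. Its R call is "ssc_propcomp (1L,ratio=1,alpha=0.05,power=0.9,p1=0.0075, p2=0.015".

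The second part takes those 4151 per arm and turns to neonatal safety. It assumes a "composite adverse neonatal outcome incidence of 1% in the revealed group, 0.5% in the concealed risk and a prespecified non-inferiority margin of 0.25" per cent, and concludes that this "would result in a power of 99% to reject the null hypothesis that the reveal strategy increases the neonatal complications". Its R call is "ssc_propcomp (3L,ratio=1,alpha=0.05,power=0.99,p1=0.005, p2=0.01, delta=0.0025". Neither call says which arm is p1 and which is p2.

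The hypothesis, in the section on induction at 37 weeks, is that screening and induction serve "to reduce the prevalence of term PE without increasing cesarean section rates or adverse neonatal outcomes". The paragraph above is the Protocol's only power statement for the neonatal part of that hypothesis.

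**The concern.** For an adverse outcome, non-inferiority means showing that the excess in the revealed arm is below the margin. The text assumes a true excess of 1% − 0.5% = 0.50 points and sets the margin at 0.25 points. Under its own planning rates the revealed strategy is inferior, so a correct test should almost never declare non-inferiority, and a larger trial would do so even less often. A power of 99% cannot come from those inputs.

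A reader is told that the trial is almost certain to settle neonatal safety. If the real power is far lower, an inconclusive neonatal result could be mistaken for evidence from a well-powered comparison.

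**Working it through.** **Inputs (all from Sample size calculation).** Revealed rate 1%, concealed rate 0.5%, margin 0.0025 (absolute, as in the delta of the R call), n = 4151 per arm, alpha 0.05. Sidedness is not stated, so one-sided 5% (z = 1.645) and one-sided 2.5% (z = 1.960) are both shown.

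**Where 4151 comes from.** Primary endpoint, unpooled variance, two-sided 5%, 90% power:

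n = (1.960 + 1.282)² × (0.0075 × 0.9925 + 0.015 × 0.985) / 0.0075² = 4150.4, hence 4151 per arm and 8302 in total. The Protocol's figure is reproduced. In this call p1 = 0.0075 is the reduced rate, that is, the revealed arm.

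**Formula for non-inferiority on a harmful outcome.**

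SE = √[(p_rev(1 − p_rev) + p_con(1 − p_con)) / n]

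Power = Φ[(margin − (p_rev − p_con)) / SE − z]

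**Rates as worded (revealed 1%, concealed 0.5%).**
- SE = √[(0.0099 + 0.004975) / 4151] = 0.001893
- (0.0025 − 0.005) / 0.001893 = −1.321
- Power = Φ(−1.321 − 1.645) = 0.15%, or Φ(−1.321 − 1.960) = 0.05%

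**Rates reversed (revealed 0.5%, concealed 1%).**
- Same SE; (0.0025 + 0.005) / 0.001893 = 3.962
- Power = Φ(3.962 − 1.645) = 98.98%, or Φ(3.962 − 1.960) = 97.7%
- The size needed for 99% at one-sided 5% is 4171 per arm, close to 4151. The stated 99% therefore rests on a distance to the margin of 0.75 points; the worded rates leave −0.25 points.

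**Equal rates (an assumption made here, not in the Protocol).**

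| Rate in both arms | SE | One-sided 5% | One-sided 2.5% |
|---|---|---|---|
| 0.5% | 0.001548 | 49% | 36% |
| 1% | 0.002184 | 31% | 21% |

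**Robustness.** With a pooled variance the worded rates still give 0.15%. With 4566 per arm (9132 / 2, including the allowance for losses) they give 0.12%. A simulation of 2 million trials per scenario, at one-sided 5%, gave 0.17% for the worded rates and 99.15% for the reversed rates. To reach 99% with the worded rates, the margin would have to be 0.005 + (1.645 + 2.326) × 0.001893 = 0.0125, or 1.25 points, five times the one stated.

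**What the R call can mean.** It has p1 = 0.005 and p2 = 0.01.
- If p1 is the revealed arm, as in the primary call, the code has revealed 0.5% and concealed 1%, and the text assigns the rates to the opposite arms.
- If p1 is the concealed arm, the code agrees with the text, but the 99% then comes from a test in the wrong direction for a harmful event.

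The Protocol does not show which was meant.

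**The case against.** The strongest reply is that two arm labels were transposed in a sentence. Read in the order of the primary call, the R syntax gives revealed 0.5% and concealed 1%, and the 99% follows. The 0.15% would then describe a slip of wording and would not be a forecast for the trial. This is possible, and the 0.15% should be read only as the result of the rates as worded. It does not rescue the paragraph: the text would still be wrong, and the 99% would rest on an undeclared assumption that the strategy halves neonatal complications. A favourable planning assumption is allowed, but a reader has to be told of it, particularly when the stated hypothesis is only that harm does not increase.

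It is also fair that the outcome is secondary, that the primary endpoint sets the sample size, and that no procedure or primary analysis depends on the 99%. That limits the consequence to this one statement.

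Two further points largely stand. A two-sided 5% level for the difference test and a one-sided 5% level for non-inferiority is common practice; sidedness is not the source of the discrepancy and deserves only a note. The equal-rates figures show sensitivity and do not themselves prove an error.

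That a statistical analysis plan may exist does not answer the point. Nothing is missing here; a printed figure contradicts its own printed inputs.

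**Conclusion.** The point holds and the paragraph must be corrected. On the rates as worded, with 4151 per arm and a 0.25-point margin, power is 0.15% (one-sided 5%) or 0.05% (one-sided 2.5%), against a stated 99%. The 99% requires the reversed rates at one-sided 5%; at one-sided 2.5% the reversed rates give 97.7%. With equal rates of 0.5% to 1% the chance of showing non-inferiority is at most about one in two.

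These figures use the normal approximation with unpooled variance and full follow-up of 4151 per arm. The conclusion does not depend on that choice, because the worded excess is larger than the margin. Whether the labels or the direction of the calculation are at fault cannot be settled from the Protocol.

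**What to change.** 1. Make text and R call agree on which arm has which rate, and label the arms in the call.
2. Restate the power that follows at 4151 per arm from the rates intended, and give the sidedness of alpha. If no neonatal benefit is assumed, wording such as this would do: *With equal event rates of 0.5% to 1%, a margin of 0.25 percentage points and one-sided alpha of 5% (2.5%), 4151 women per arm give 49% to 31% (36% to 21%) power.*
3. If the 99% is kept, say openly that it assumes the revealed strategy halves neonatal complications (0.5% against 1%) at one-sided 5%, and give the reason for expecting this.
4. In the same sentence, say which composite the assumed rates refer to.

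The cost is one paragraph of Protocol wording and one restated figure. No patients are added and no outcome definition changes. The stated power becomes less favourable unless the halving is declared.

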**PE37: A multicenter randomized trial of screening with sFlt1/PIGF and selective labor induction to prevent preeclampsia at term.**

Primary Site:
 
BCNatal (Hospital Clínic and Hospital Sant Joan de Déu) and Hospital Sant Pau, Barcelona, Spain

Principal Investigators:
 
[name], [name] and [name]

Disease Studied and Intervention
 
Preeclampsia in late pregnancy

Cohort:
 
Non-selected nulliparous pregnant women routinely attended at 35-36 weeks' gestation and randomized to revealed versus concealed maternal angiogenic factors levels.

Inclusion and Exclusion Criteria:
 
Inclusion criteria:
 
 
1. Nulliparous women
 
2. Singleton pregnancies
 
3. >18 years old
 
4. 35.0-36.6 weeks of gestation
 
5. Maternal written consent form
 
6. Planned vaginal delivery
 
 
Exclusion criteria:
 
-Any maternal or fetal complications that require labor induction before 38 weeks according to local institutional protocols (including established preeclampsia).

Study Type
 
Prospective, open-label randomized multicentre study with parallel groups conducted at BCNatal (Hospital Clínic and Hospital Sant Joan de Deu) (Barcelona), Hospital Sant Pau (Barcelona), Hospital la Paz (Madrid), Hospital del Mar (Barcelona), Hospital la Fe (Valencia), Hospital Son Llatzer (Mallorca), Hospital Can Ruti (Badalona), Hospital Clínico de Zaragoza, Hospital Arrixaca de Murcia and Complejo Hospitalario Universitario Insular Materno Infantil (Las Palmas de Gran Canaria) (Spain), Institute for the Care of Mother and Child, Prague, Prague, Czechia, Centre of Postgraduate Medical Education, Obstetrics and Gynecology and Perinatal Medicine, Warsaw, Poland;

Gynecology and Obstetrics - CHU Liège; Belgium.

Intervention
 
 
Revealed arm: Blood sampling at 35+0-36+6w to determine sFlt-1/PlGF ratio. The result will be known by managing clinicians and, if >90th centile, labour induction from 37+0 weeks will be offered.
 
Concealed arm: The result of sFlt1/PlGF ratio will be unknown. Routine follow-up
 

Duration
 
3 years

Date Of First Enrolment
 
February 2021

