### **Justification of the study**

Finding an effective prediction and prevention for term PE remains an unsolved challenge. From previous recent evidence it seems clear that prediction very close to term may achieve a high detection rate, but there is no evidence as to which strategy might be effective in preventing PE in high-risk women. The investigators postulate that a solution that would be applicable in most settings worldwide would require a simplified, pragmatic, approach. The rationale of this proposal is that PE could be reduced with a single-step lab test screening followed by induction of labor (IOL).

**A single-step lab measure to detect PE.** Combined algorithms using angiogenic factors with Doppler ultrasound and maternal features seem to achieve the highest performance in detecting pre-clinical PE. However, the need to train staff and change pregnancy care protocols renders difficult generalization in high-resource and even more low-resource settings. On the contrary, single lab tests can be more easily incorporated into the mainstream clinical practice and provide a widespread solution for high-resource settings and specially sub-optimal healthcare systems heavily affected by the consequences of term PE. Angiogenic factors are the obvious candidate for these purposes. The sFlt1/PIGF ratio at 35-36w predicts term PE with a DR of 82% and is a standardized lab test nowadays, realizable by ELISA with widely available automated lab platforms. Normal values in late pregnancy have been reported and are fairly similar among different populations. As preliminary research for this study, the investigators have confirmed that the gestational-age adjusted normal values of sFlt1/PIGF matched quite remarkably those previously published in different populations across Europe. A one-step screening with sFlt1/PIGF would select a 5-10% of the population with the highest risk for PE.

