### Objectives

To evaluate the impact of a policy of induction of labour from 37 weeks of gestation in nulliparous women at risk for preeclampsia as defined by a sFlt1/PIGF ratio >90th centile at 35-36 weeks of gestation on the prevalence of term PE.

As secondary objectives, the study will evaluate the impact of the sFlt1/PIGF screening on:

1. Cesarean section rates
2. Perinatal morbidity
3. Maternal pregnancy-related morbidity.
4. Maternal post-pregnancy endothelial function.
5. Cost-efficiency analysis (hospital maternal and neonatal stay and incurred costs).
6. Maternal experience.

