#### Study population:

Non-selected nuliparous pregnant women routinely attended at 35-36 weeks' gestation and randomized to revealed versus concealed maternal angiogenic factors levels.

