### **Randomization**

This will be an open-label randomized trial with parallel groups. An online service (<http://www.clinapsis.com>) will be used to generate a randomised sequence for the block of 1000 participants.

The allocation will be sequestered internally by a Clinical Trials Unit. After enrolment, recruiting physicians will obtain the allocation group from the Unit. Due to the nature of the interventionism it is not possible to blind participants or physicians from the Obstetric Department; however, obstetric management will follow similar protocols in each of the participating centers.

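### Is it a fault that neonatal safety is sized on whole arms when only about 5-10% of women are offered induction for the ratio?

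*Protocol*

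**What the plan says.** The Objectives section sets the question at the level of a strategy: "To evaluate the impact of a policy of induction of labour from 37 weeks of gestation" in nulliparous women whose ratio puts them at risk. The section on induction at 37 weeks adds a safety half to the hypothesis, that term preeclampsia falls "without increasing cesarean section rates or adverse neonatal outcomes".

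The Sample size calculation sizes neonatal safety once, on whole arms. It assumes 1% with the composite in the revealed group, "0.5% in the concealed risk and a prespecified non-inferiority margin of 0.25%; this sample size (4151 per arm"), and claims 99% power. No caesarean rate or caesarean sizing is given. The Statistical analysis section analyses women by assigned group; its text breaks off mid-sentence in the copy at hand.

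Induction for the ratio is offered only in the revealed arm and only above the 90th centile. The Justification of the study says a one-step screen "would select a 5-10% of the population with the highest risk for PE".

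On measurement, the synopsis Intervention row reads "Revealed arm: Blood sampling at 35+0-36+6w to determine" the ratio. For the concealed arm it says the "ratio will be unknown. Routine follow-up". The Study population section describes women "randomized to revealed versus concealed maternal angiogenic factors levels".

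**The concern.** Two things look wrong.

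The first is dilution. At least nine in ten revealed-arm women are not offered induction for the ratio. If harm falls only on those who are, the whole-arm difference is that harm multiplied by a share of 0.05 to 0.10. A small whole-arm margin, or a caesarean comparison showing no difference, could then sit beside a sizeable excess in the women the intervention reaches.

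The second is measurement. Blood sampling is written out for the revealed arm only. If the concealed arm were never sampled, women above the cut-off could not be compared as randomised, and no later analysis plan could restore that comparison.

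At stake is whether a reader could judge safety in the women who are offered early induction.

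**Working it through.** **1. The plan's own figures.** Inputs are from the Sample size calculation.

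- Primary endpoint, 0.75% against 1.5%, two-sided 5%, 90% power, unpooled variance: n = (1.960 + 1.282)² × (0.0075×0.9925 + 0.015×0.985) / 0.0075² = 4150.4, so 4151 per arm, 8302 in all. It reproduces.
- Neonatal non-inferiority: standard error = √[(0.005×0.995 + 0.01×0.99)/4151] = 0.00189. The stated 99% appears only if the margin is added to the assumed harm: 0.0075/0.00189 − 1.645 = 2.32, power 98.98%. In the direction the text states, the distance is 0.0025 − 0.005 = −0.0025 and the chance of success is about 0.15%. That is a fault of the rates and margin. It would be the same whatever group were analysed.

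**2. Size of the dilution.** Assume women below the cut-off are unaffected. Equivalent above the cut-off = whole-arm difference / share.

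| Share | Margin 0.25 points | Assumed benefit 1.5 − 0.75 = 0.75 points | Margin / benefit |
|---|---|---|---|
| 5% | 5.0 | 15.0 | 1/3 |
| 10% | 2.5 | 7.5 | 1/3 |

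Harm and benefit scale together, so dilution does not make the margin loose relative to what the strategy is meant to gain. The 10% row fits the operative rule better: the cut-offs (25 at 35 weeks, 35 at 36 weeks) are the 90th centile of 600 uneventful pregnancies, which implies about 10% or more in unselected women if that reference carries over.

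**3. Whether the whole-arm test lets harm through.** One-sided 5%, 4151 per arm, concealed rate 0.5%, 10% share:

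- no true excess: passes 48.8% of the time;
- 1 point above the cut-off (0.10 overall): 23.6%;
- 2.5 points above the cut-off (0.25 overall): 5.0%.

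A harm equal to the margin is passed no more often than the test's nominal error rate.

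**4. What a comparison above the cut-off would add.** With 4151 × 0.10 ≈ 415 women per arm and full uptake:

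- 95% half-width at 0.5% in both arms: 1.96√(2×0.005×0.995/4151) = 0.30 points overall, or 3.0 rescaled by 1/0.10. Directly, 1.96√(2×0.005×0.995/415) = 0.96 points, a ratio of about 3.2. If the baseline above the cut-off is 2% (assumed), the direct half-width is 1.90 and the ratio falls to 3.03/1.90 = 1.6.
- Neonatal power, two-sided 5%, normal approximation (Fisher), at baselines of 0.5%, 1% and 2%: a 2.5-point rise has 79%, 68% and 53% (75%, 63%, 47%); a 1-point rise has 30%, 22% and 15% (18%, 14%, 11%). At a 5% share (208 per arm) a 2.5-point rise has 49%, 41% and 30% (34%, 28%, 21%).
- Caesarean, with a base rate of 20-30% assumed because the Protocol gives none: a 10-point rise has 17-20% power on whole arms and 86-92% directly; a 5-point rise has 8-9% and 34-41%.

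The gain is real for large effects and slight for small neonatal ones.

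**5. Whether the concealed arm is measured.** The synopsis Cohort row uses the same words as the Study population section, so both describe concealed levels. The synopsis concealed-arm entry says the result will not be known, which presupposes a result. The Executive summary separates the arms by whether clinicians know the ratio. Set side by side, these describe one measurement in every woman, disclosed in one arm and withheld in the other. The sampling phrase under the revealed arm adds a detail there and denies nothing about the concealed arm.

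**The case for a change.** The strongest case for the concern is that safety is part of the stated hypothesis and the women who bear any risk are few. A null whole-arm caesarean result would say little about them: for a 10-point rise the whole-arm comparison has 17-20% power against 86-92% directly. No sentence states outright that a concealed-arm sample is taken and assayed, and an untaken sample cannot be recovered.

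The arithmetic stands, and so does the missing explicit sentence. Neither makes the plan wrong.

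- Whole arms answer the policy question. They also capture any change in the care of women told their ratio is normal, which matters because "it is not possible to blind participants or physicians from the Obstetric Department". A comparison above the cut-off would miss that, so it could only support the main one.
- A supporting table in a marker-defined subgroup, or a margin restated on that scale, is ordinary content for an analysis plan. Its absence from a protocol whose analysis section is cut short shows nothing.
- The precision gain for the neonatal outcome depends on the baseline above the cut-off. The composite in Outcome variables includes birth weight below the 3rd centile, so that baseline may exceed 2%. At an assumed 3% against 5.5% with 415 per arm, power is about 43%. Incomplete uptake lowers every figure.
- A sentence confirming that both arms are assayed would be a useful clarification. Its absence does not set one section against another.

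**Conclusion.** The concern does not hold. Whole-arm intention-to-treat is the right basis for a screening-policy objective. The dilution is genuine: 0.25 points corresponds to 2.5 points above the cut-off at a 10% share and 5 at 5%, if other women are unaffected. It applies equally to the assumed benefit and leaves the margin at one third of it. The sections on measurement agree on their natural reading. A direct comparison above the cut-off would inform on large harms (79% power at best for a 2.5-point neonatal rise at a 10% share) but not small ones (11-30% for 1 point). It would leave the main safety conclusion as it is. Whether to add it is a matter of preference and may already be settled in the analysis plan.

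This rests on reading concealed levels as measured levels, on the Protocol's 5-10% share, and on assumed baselines and full uptake for the power figures. It does not clear the neonatal non-inferiority calculation itself: an assumed difference of 0.5 points against a margin of 0.25 points is a separate and more serious fault.
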